**Prospective Randomized comparison Of prosthetic Valve Effective
orifice area: One-year analysis of two bovine PERIcardial valves
(PROVE-PERI trial)**

NCT 03796442

Trial Protocol v 1.4

Updated Dec 28, 2018

Protocol summary

Trial name and number	Prospective Randomized comparison Of prosthetic Valve Effective orifice area: One-year analysis of two bovine PERIcardial valves (PROVE-PERI trial) ClinicalTrial.gov 03796442
Objectives	This randomized controlled trial is designed to compare 1-year hemodynamic performances and clinical outcomes after aortic valve replacement (AVR) using a recently introduced and world-wide used bovine pericardial bioprostheses.
Design	Prospective randomized controlled trial
Study periods	IRB approval date ~ June 30, 2022
Subjects	Patients who are scheduled to undergo AVR
Sample size	Total 140 patients
Methods	Patients over 19 years of age who are scheduled to undergo AVR on a nonemergency basis and who are planned to undergo primary AVR using stented bioprostheses are assessed for eligibility for study enrollment. The exclusion criteria include (1) patients with concomitant mitral or tricuspid valve operation, (2) patients with infective endocarditis, (3) patients with severe left ventricular dysfunction (ejection fraction < 0.30), (4) patients with a medical history such as a malignant disease that might limit the possibility of mid-term follow-up and (5) patients who refuse study enrollment. Enrolled patients are randomly assigned to 1 of the 2 bioprostheses in a 1:1 manner. After surgery, early clinical and hemodynamic outcomes are evaluated following the protocol. After discharge, all patients undergo regular postoperative follow-up and are evaluated with echocardiography at 1-year follow-up.
Endpoints	The primary endpoint of the PROVE-PERI trial was mean pressure gradient across the aortic valve (AVMPG) on 1-year echocardiographic follow-up. The secondary endpoints were the effective orifice area (EOA) on 1-year echocardiographic follow-up and 1-year clinical outcomes including all-cause mortality, cardiac death and major adverse event (MAEs).
Safety	Postoperative complications including operative mortality, low cardiac output, bleeding reoperation, perioperative myocardial infarction, perioperative stroke, acute kidney injury, respiratory complications, postoperative atrial fibrillation, and mediastinitis were monitored for safety.

The Avaluus™ (Medtronic, Minneapolis, MN) is one of most recently introduced stented bovine pericardial bioprostheses. [2] A prospective observational study, which is called PERIGON (PERIcardial SurGical AOrtic Valve ReplacemeNt) Pivotal Trial, have reported favorable 5-year hemodynamic performance and clinical outcomes after AVR using the Avaluus™ valve.⁴ However, there has been no study that prospectively compared results after AVR using the Avaluus™ with those after AVR using other bovine pericardial valves.

To perform a comparative analysis for the efficacy and safety of this newly introduced bioprosthetic, a prospective randomized controlled trial (RCT) comparing the Avaluus™ with the world-wide used Carpentier-Edwards PERIMOUNT Magna Ease (CEPME; Edwards Lifesciences, Irvine, CA) was designed by the authors.

2) Hypothesis and Objectives

The present study is conducted to compare 1-year hemodynamic performances after AVR using the AvaluTM valve with those using the CEPME.

We hypothesize that the AvaluTM was noninferior to the CEPME based on the mean pressure gradient across the aortic valve (AVMPG) at 1-year echocardiographic follow-up.

9. Inclusion criteria, Exclusion criteria and Sample size calculation

1) Inclusion criteria

- ① Patients who are scheduled to undergo AVR
- ② Over 19 years of age
- ③ Patients who are planned to receive a bioprosthetic valve for aortic valve substitute
- ④ Patients who or whose legal representative fill out a written consent form before the start of the clinical trial and patients who can comply with the clinical trial requirements

2) Exclusion criteria

- ① Patients with concomitant mitral or tricuspid valve operation
- ② Patients with severe left ventricular dysfunction (ejection fraction < 0.30)
- ③ Patients with infective endocarditis
- ④ Patients with a medical history such as a malignant disease that might limit the possibility of mid-term follow-up
- ⑤ Patients who refused study enrollment

3) Sample size calculation

The study is designed to have 80% power to detect 1-year AVMPG of 12.6 ± 4.3 mmHg for the study prosthesis [2] and 11.9 ± 4.3 mmHg for the control prosthesis, [3-5] with a 1-sided type I error of 2.5% and a noninferiority margin of 3 mmHg. The noninferiority margin is determined by the values of 15 mmHg for AVMPG of clinically significant aortic stenosis [6] and 12 mmHg for AVMPG of the control prosthesis. Fifty-six patients in each group are needed to complete the study cohort. Allowing for a 20% dropout rate during the 1-year follow-up, we determine that the recruitment of 70 patients in each group is necessary.

- (1) Level of significance (α) = 0.025
- (2) Type II error (β) = 0.20, power of the test = 80%
- (3) Drop out rate = 20%
- (4) One-tailed test

H_0 (null hypothesis): $\mu_1 - \mu_2 \geq \delta$

H_1 (alternative hypothesis): $\mu_1 - \mu_2 < \delta$

(μ_1 : mean AVMPG of the study group on 1 – year echocardiographic follow – up ,

μ_2 : mean AVMPG of the control group on 1 – year echocardiographic follow – up

δ : noninferiority margin)

The calculation was performed using PASS Software(Power Analysis and sample size software: <http://www.ncss.com>), and the calculated formula is as follows.

$$n = \frac{(Z_\alpha + Z_\beta)^2 (\sigma_1^2 + \sigma_2^2)}{((\mu_1 - \mu_2) - \delta)^2}$$

μ_1 = mean AVMPG of the study group on 1 – year echocardiographic follow – up

μ_2 = mean AVMPG of the control group on 1 – year echocardiographic follow – up

σ_1 = standard deviation of AVMPG of the study group on 1 – year echocardiographic follow – up

σ_2 = standard deviation of AVMPG of the control group on 1 – year echocardiographic follow – up

δ : noninferiority margin

4) Subject recruitment plan

Subject recruitment will be performed for the patients who are scheduled to undergo AVR and who are hospitalized at Seoul National University Hospital and Seoul National University Bundang Hospital after providing sufficient explanation and informed consents. The subjects will be recruited competitively.

10. Methods

1) Detailed process of the study

Patients over 19 years of age who are scheduled to undergo AVR on a nonemergency basis and who are planned to undergo primary AVR using stented bioprostheses at 2 institutions are assessed for eligibility for study enrollment. After excluding the patients who meet the exclusion criteria and who refuse to participate, enrolled patients are randomly assigned to 1 of the 2 bioprostheses in a 1:1 manner.

Surgeries are performed under median sternotomy or upper partial sternotomy under cardiopulmonary bypass with cold cardioplegic arrest. After the diseased AV is excised, the annulus is prepared for landing the prosthesis, and the proper valve sizes for both types of

prostheses are decided before randomization. Then, randomization is performed with a web-based block randomization method with randomly determined block sizes of 4 and 6. After randomization, the assigned prosthesis is implanted with non-everting transverse mattress sutures. The knot-tying is performed manually or by using an automated knot-fastener.

Patients are evaluated with early clinical outcomes and early echocardiographic measurements. After discharge, all patients undergo regular postoperative follow-up through the outpatient clinic at 3- to 6-month intervals and are interviewed by telephone for confirmation of their condition if the last clinic visit has not been conducted as scheduled. At postoperative 1-year, clinical outcomes and echocardiographic measurements are evaluated as scheduled.

※ Randomization : Patients who meet the inclusion criteria and the exclusion criteria are randomly assigned to 1 of the 2 bioprostheses in a 1:1 manner. Randomization is performed with a web-based block randomization method (<https://mrcc.snuh.org/>) with randomly determined block sizes of 4 and 6, considering the institution as a stratification factor.

2) Outcome measures

- 1) Demographics: age, sex, height, weight, BMI, BSA, diagnosis, operation name
- 2) Preoperative data
 - Risk factors: DM, HTN, smoking, dyslipidemia, stroke, COPD, CKD, chronic liver disease, coronary disease, peripheral vascular disease, history of cardiac surgery, New York Heart Association functional class, STS mortality risk, EuroSCORE II
 - Echocardiographic measurements: Effective orifice area, mean pressure gradient, peak pressure gradient, LA dimension, LV ejection fraction, LV end diastolic dimension, LV end systolic dimension, pulmonary artery systolic pressure, TR severity, etc.
 - Electrocardiography
 - Laboratory tests: CBC, routine chemistry, NT-proBNP, CRP, ABGA, lactate, PT, aPTT
 - CT scan (thoracoabdominal CT angio)
 - Pulmonary function test
- 3) Operative data: CPB time, ACC time, concomitant procedures, operative findings
- 4) Postoperative data
 - Early clinical outcomes: op mortality, op morbidities (low cardiac output, bleeding reoperation, perioperative myocardial infarction, perioperative stroke, acute kidney injury, respiratory complications, postoperative atrial fibrillation, and mediastinitis)

- Echocardiographic measurements: Effective orifice area, mean pressure gradient, peak pressure gradient, LA dimension, LV ejection fraction, LV end diastolic dimension, LV end systolic dimension, pulmonary artery systolic pressure, TR severity, etc.
- Electrocardiography: 1st, 2nd and 3rd AV block, bundle branch block

5) 1-year follow-up data

- Clinical outcomes: all-cause mortality, cardiac death and major adverse events (valve-related mortality, structural valve deterioration, nonstructural dysfunction, thromboembolic and bleeding events, prosthetic valve endocarditis, AV reintervention or the need for a new permanent pacemaker or defibrillator within 14 days after the index operation), last follow-up date, New York Heart Association functional class
- Echocardiographic measurements: Effective orifice area, mean pressure gradient, peak pressure gradient, LA dimension, LV ejection fraction, LV end diastolic dimension, LV end systolic dimension, pulmonary artery systolic pressure, TR severity, etc.
- Electrocardiography: 1st, 2nd and 3rd AV block, bundle branch block

※ Primary clinical endpoint

mean pressure gradient across the aortic valve (AVMPG) on 1-year echocardiographic follow-up

※ Secondary clinical endpoint

the effective orifice area (EOA) on 1-year echocardiographic follow-up

operative mortality, operative morbidities

1-year clinical outcomes (all-cause mortality, cardiac death and major adverse events)

3) Differences from previous treatments and studies

When compared with previous treatments, the operative strategies and perioperative management are identical, but only the bioprostheses used in the treatments are different.

When compared with previous studies, all studies previously performed were prospective single-arm designs or retrospective studies. To the best of our knowledge, the present study is the first prospective randomized controlled trial comparing results of AVR using the Avaluus™ valve with those using another bovine pericardial valve that has been used worldwide.

4) Risks associated with the study

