Statistical analyses will be performed using SPSS software (version 25.0; IBM, Armonk, NY) and SAS software (version 9.3; SAS Institute, Cary, NC). Data will be expressed as the mean \pm standard deviation, median with IQRs or proportions. Comparisons between the 2 groups will be made using the chi-square test and Fisher's exact test for categorical variables and Student's t-test or the Mann-Whitney test for continuous variables, as appropriate. The null hypothesis is that the AvaluTM is inferior to the CEPME based on the AVMPG at 1-year echocardiographic follow-up, with a non-inferiority margin of 3mmHg. The result for the primary endpoint is presented with 97.5% one-sided confidence interval for mean difference between groups. The non-inferiority test will be performed using a t-test which compares mean difference between groups with the non-inferiority margin under the one-sided significance level of 0.025. For analysis of 1-year clinical outcomes including all-cause mortality, cardiac death, and MAEs, events will be counted at postoperative 1 year, and comparisons between the 2 groups will be made using the chi-square test and Fisher's exact test. A P value of $< .050$ will be considered statistically significant. All outcomes will be compared with an intention-to-treat base. Per-protocol and as-treated analyses will be added for hemodynamic outcomes.

References

3. D Rennie. How to report randomized controlled trials. The CONSORT statement. *JAMA.* 1996;276:649.
4. Fiegl K, Deutsch MA, Rondak IC, Lange R, Guenzinger R. Matched Comparison of Two Different Biological Prostheses for Complete Supra-annular Aortic Valve Replacement. *Thorac Cardiovasc Surg.*

2015;63:459-66.

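### As the plan is written, the valve sizes chosen for both prostheses before randomisation are neither recorded before allocation, nor named in the data lists, nor used in the primary AVMPG analysis

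*Protocol*

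**What the plan says.** **Order of events.** Protocol section 10.1 places sizing after the diseased valve has been excised and the annulus prepared. The sizes for both types of valve are settled first: the "prostheses are decided before randomization. Then, randomization is performed with a web-based block randomization method". Blocks are of random size 4 or 6, stratified by institution. The allocated valve is then implanted. The section describes no step at which either size is entered or written down before the allocation is shown. It does not say that the implanted size must match the pre-chosen one, or how a difference is handled.

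**Data collected.** The intraoperative list in Protocol section 10.2 reads in full: "Operative data: CPB time, ACC time, concomitant procedures, operative findings". No list in that section (demographic, preoperative, operative, postoperative or one-year) names a pre-chosen size, an implanted size or an annulus diameter. The open items for operative findings and operation name could hold the implanted size.

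**Primary analysis.** The SAP states: "The non-inferiority test will be performed using a t-test which compares mean difference between groups with the non-inferiority margin". Protocol section 10.7 gives the same test. Neither includes a covariate. Section 10.7 also requires the ITT and per-protocol analyses both to confirm noninferiority. The per-protocol set removes major protocol violations, which are not defined.

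**The concern.** The primary endpoint is a gradient across the implanted valve, so the size implanted is an obvious candidate predictor of it. The surgeon knows the valve type when implanting. Deciding both sizes beforehand is a good safeguard, because it keeps the initial sizing independent of the allocation. Two things are left on the table.

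- **Verification.** If the two sizes are not captured before allocation, the listed data cannot show that the implanted size was the one chosen blind to allocation. An implanted size noted under operative findings would help only in part. It exists only for the allocated valve, arises after randomisation, and says nothing about what had been chosen for the other valve. The per-protocol analysis does not clearly help either, since a sizing departure is neither named as a major violation nor ruled out as one. The as-treated analysis, if it groups patients by the valve received, would not address size.
- **Precision.** Each pre-chosen size exists for every patient in both arms and is fixed before allocation. Each is therefore a genuine baseline covariate, available at almost no cost, and the primary comparison does not use it.

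**Working it through.** **Inputs from the documents (Protocol section 9.3, repeated in the SAP)**
- "Level of significance (α) = 0.025", one-sided; power 80%; margin 3 mmHg.
- Assumed means and SDs: "12.6 ± 4.3 mmHg for the study prosthesis" and "11.9 ± 4.3 mmHg for the control prosthesis", so the assumed true difference is 12.6 − 11.9 = 0.7 mmHg and the distance to the margin is 3 − 0.7 = 2.3 mmHg.
- 56 completers and 70 recruited per group, with 20% dropout.

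**Inputs not in the documents (assumptions)**
- R², the share of AVMPG variance explained by pre-allocation size: 5%, 10% or 20%.
- Any net shift in the group difference caused by size changes after allocation: 0.2 or 0.4 mmHg in either direction.

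**Step 1. Reproduce the stated sample size.**
- Normal formula: n = (1.960 + 0.842)² × (4.3² + 4.3²) / 2.3² = 54.87, so 55 per group.
- Non-central t: power is 79.4% at 55 and 80.1% at 56, so 56 per group.
- Dropout: 56 / (1 − 0.20) = 70.

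The stated figures reproduce.

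**Step 2. Precision gained by adjustment, 56 per arm.** Residual SD = 4.3 × √(1 − R²); SE = residual SD × √(2/56). Power is from the non-central t with noncentrality 2.3/SE. Half-width is t(0.975, 110 df) × SE = 1.982 × SE, the distance from the estimate to the one-sided 97.5% bound.

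| Assumed R² | Residual SD | SE | Power | Half-width (mmHg) |
|---|---|---|---|---|
| 0 | 4.300 | 0.813 | 80.1% | 1.61 |
| 5% | 4.191 | 0.792 | 82.1% | 1.57 |
| 10% | 4.079 | 0.771 | 84.1% | 1.53 |
| 20% | 3.846 | 0.727 | 88.0% | 1.44 |

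Using 108 degrees of freedom, to allow for one size term and one institution term, changes power by no more than about 0.01 percentage points.

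**Step 3. Illustration of a net sizing shift.** Let the true difference equal the 3 mmHg margin, and let size changes after allocation move the expected difference by b mmHg in favour of the study valve (negative b favours the control). With SE = 4.3 × √(2/56) = 0.813, the one-sided error is approximately 1 − Φ(1.960 − b/0.813).

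| b (mmHg) | b/SE | One-sided error |
|---|---|---|
| +0.4 | 0.492 | 7.1% |
| +0.2 | 0.246 | 4.3% |
| 0 (no changes, or equal effect in both arms) | 0 | 2.5% |
| −0.2 | −0.246 | 1.4% |
| −0.4 | −0.492 | 0.7% |

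No passage supplies a value of b or suggests that such changes will occur. The table shows only how sensitive the test would be.

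**The case against.** Several points on the other side stand.

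- **The plan already has the main safeguard.** Both sizes are decided on the prepared annulus before a web-based allocation with random block sizes. Nothing in the documents suggests that sizes will be altered afterwards.
- **Silence is not absence.** The case report form and the web form are not among the documents. A reader might infer that size is not recorded at all, that a change would leave no trace, or that the safeguard can never be checked. The documents do not support that. They show only that the plan does not state that the sizes are captured. What survives is that the listed items, even read generously, would not show what had been chosen for both valves before allocation.
- **The primary test is sound.** A reader might infer that omitting size biases the comparison or leaves the trial underpowered. Neither follows. The unadjusted t-test is valid under randomisation, and the sample size built for it reproduces. How strongly size predicts AVMPG is not stated; at an R² of 5% the gain is about two percentage points.
- **An inflated error rate is not shown.** The shifts are hypothetical and may go either way or cancel. A size changed because the allocated valve does not seat as expected is arguably part of the effect of assignment, which an ITT analysis is meant to include. It would then not be bias at all. This is a reason to record changes with their reasons, not to forbid them.

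The objections limit the point to verification and precision. They do not remove it, because the sizes are already determined for every patient and, if not captured before allocation, cannot be reliably reconstructed later.

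**Conclusion.** The point holds as a cheap improvement, not as an error in the design. The plan creates two baseline size values per patient but, as written, does not require them to be entered before allocation, does not name them in the data lists and does not use them in the primary analysis.

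The consequence is lost precision, and the inability to confirm from the listed data that sizing was independent of allocation. Under an assumed R² of 5% to 20%, the precision at stake is 2 to 8 percentage points of power at 56 per arm, or 0.04 to 0.17 mmHg of CI half-width. These figures rest on the plan's own SD, margin and assumed difference; the R² range is an assumption. The error-rate figures are illustrative only and make no claim that the trial's type I error departs from 2.5%.

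**What to change.** 1. **Protocol 10.1.** Make both pre-chosen sizes (Avalus and CEPME) required fields on the web randomisation form, to be completed before the allocation is returned.
2. **Protocol 10.2, operative data.** Add the two pre-chosen sizes, the implanted size, and a flag with reason where the implanted size differs from the one pre-chosen for that valve. Report these differences by arm. This records the surgeon's choice and does not restrict it.
3. **Protocol 10.7 and SAP.** Prespecify the primary AVMPG analysis as a linear model on arm, institution (the stratification factor) and one pre-allocation size on a scale common to both arms, for example the CEPME size chosen in every patient. Test the arm coefficient against 3 mmHg at one-sided 2.5%. Keep the unadjusted t-test as a sensitivity analysis. Do not adjust for implanted size, which arises after randomisation and is known only for the allocated valve. State how a missing pre-allocation size is handled; required fields should make this rare.

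The cost is two fields on an existing form, a few operative items, some SAP text, a few seconds of entry in theatre and a few degrees of freedom. No extra patients or procedures are needed, and the sample size can stay as it is.

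### The protocol publishes its small block sizes although the operator knows each implanted valve and sizing precedes randomisation; the sizes belong in a restricted file

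*Protocol*

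**What the plan says.** Protocol Section 10, item 1 (Detailed process of the study) gives the block sizes twice. The running text says "Then, randomization is performed with a web-based block randomization method with randomly determined block sizes of 4 and 6". The randomisation note repeats them and adds the stratum: "with randomly determined block sizes of 4 and 6, considering the institution as a stratification factor". Section 9, item 4 names two hospitals.

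The order of events is also in Section 10.1. The diseased valve is excised, the annulus is prepared, and the proper sizes for both types of "prostheses are decided before randomization". The web call follows, and the assigned valve is then implanted.

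In the text available to me, nothing says who can view past allocations, how many surgeons operate at each hospital, or whether the block parameters are kept from the operators. The SAP does not discuss randomisation. Part of the protocol was not available, so this silence does not prove absence.

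**The concern.** Choosing both sizes before the allocation is known is a good safeguard against sizing one valve more favourably than the other. It works fully only if the coming arm is unpredictable at that moment. In small blocks within a hospital, each completed block is balanced, so anyone who has counted the implanted valves knows which arm is behind. If the maximum block size is also known, some allocations become certain.

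A guess could influence which patient is put forward or how the annulus is sized for each valve. Either would pass into the primary comparison, which is an unadjusted t-test of 1-year AVMPG against a 3 mmHg margin. A shift favouring the study valve raises the chance of a false noninferiority conclusion. Requiring both ITT and PP to agree would not help, because both would carry the same shift. A shift favouring the control would instead make noninferiority harder to show.

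**Working it through.** **1. The plan's own figure.** Section 9, item 3 gives "Level of significance (α) = 0.025", "One-tailed test", 80% power, margin 3 mmHg, "1-year AVMPG of 12.6 ± 4.3 mmHg for the study prosthesis" and "11.9 ± 4.3 mmHg for the control prosthesis". The assumed difference is 12.6 − 11.9 = 0.7, so the distance to the margin is 3 − 0.7 = 2.3.

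- Normal formula: n = 2 × [4.3 × (1.960 + 0.842) / 2.3]² = 54.87, so 55 per arm.
- Exact t-test power: 79.4% at 55 and 80.1% at 56, so 56 is right for the t-test.
- Dropout: 56 / 0.8 = 70 per arm.

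The sample size reproduces. The documents give no figure for predictability.

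**2. Predictability.** Assumptions: sizes 4 and 6 equally likely (the mix is not stated) and 70 patients per hospital (the split is not stated). The simulated observer knows the sizes and updates the probability of the next arm by Bayes' rule from the allocations seen at that hospital.

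| Observer | Correct guesses | Certain allocations |
|---|---|---|
| Sees all | 69.2% | 5.5% |
| Sees 75% | 62.4% | 1.3% |
| Sees 50% | 58.6% | 0.2% |
| Sees 25% | 54.9% | under 0.1% |

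Chance is 50%. With full view, 49% of allocations can be called with at least 75% probability. Full-view results change little with other assumptions: 68.9% to 69.2% correct for 30 to 110 patients per hospital, and 68.5% to 69.9% for size mixes from 25:75 to 75:25. The certain share ranges from 2.7% to 8.1% across those mixes.

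**3. What publication adds.** Guessing whichever arm is behind, without knowing the sizes, gives 69.1% with full view. Knowing the sizes therefore does not raise the average hit rate; it adds the certain calls. For example, an imbalance of 3 can arise only in a block of 6 that opened with three of one valve, so the remaining three allocations are forced. The chance of such an opening in a block of 6 is 2/20 = 0.10. With half the blocks of size 6 and a mean block size of 5, this accounts for 0.5 × 0.10 × 3 / 5 = 3.0% of allocations. The other 2.5 points come from other sequences that reveal a block's size or position.

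**4. Possible effect on the primary test.** Let p be the share of correct guesses. Suppose a guess of the study valve shifts expected AVMPG by −v, and a guess of the control by +v. The mean shift is −v(2p − 1) in the study arm and +v(2p − 1) in the control arm, so the bias in the difference is 2v(2p − 1) in favour of the study valve. With 56 per arm, SE = 4.3 × √(2/56) = 0.813. The one-sided error at the margin is Φ(−1.960 + bias/SE).

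| v (assumed) | p | Bias, mmHg | Error |
|---|---|---|---|
| 0.25 | 0.692 | 0.19 | 4.2% |
| 0.5 | 0.692 | 0.38 | 6.8% |
| 0.25 | 0.586 | 0.09 | 3.2% |
| 0.5 | 0.586 | 0.17 | 4.0% |

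**5. Alternatives, full view.**

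- A 6/8/10 mix: 66.1% correct and 1.6% certain even if the sizes are known. At v = 0.5 the bias is 2 × 0.5 × 0.322 = 0.32 mmHg and the error 5.9%.
- A big-stick rule (simple randomisation until the imbalance reaches 4): 11.4% of allocations are forced, so correct guesses are 0.5 + 0.5 × 0.114 = 55.7%. At v = 0.5 the error is 3.4%.

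**The case against.** The strongest reply is that the plan is already better protected than many. Block size varies at random, which cuts certain calls to 5.5% from 32% with fixed blocks of 4 or 24% with fixed blocks of 6. Allocation is web-based and takes place during the operation, with both sizes already settled on the prepared annulus. Consent comes earlier, so choosing patients by predicted arm would also require forecasting the order of operations. All of this stands.

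A reader might infer that the surgeons see every past allocation. The documents do not say so. An operator knows the valves he or she implanted, but knowing a colleague's is an inference, and 69% is an upper case. The 59% for a half view also assumes a careful calculation; someone who merely counts the half seen gets about 54%.

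A reader might also infer that publication creates the 69%. It does not: counting alone achieves it, and publication adds only the certain calls.

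Finally, v is an assumption. The documents give neither a motive to favour the study valve nor evidence that anyone would act on a guess. At v = 0.5, patients guessed for the two arms already differ by 1 mmHg, more than the planned valve difference of 0.7 mmHg.

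**Conclusion.** The point holds as a modest, avoidable weakness in concealment. Small block sizes are printed in the protocol of a trial where the operator knows the implanted valve and selection and sizing precede the allocation. With full view of a hospital's allocations, about 69% of guesses would be correct and about 5.5% of allocations certain; with half view, about 59% and 0.2%. These figures rest on an equal mix of sizes and 70 patients per hospital, and the hit rates barely move when either is varied.

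The error rates of 4.2%–6.8% (full view) and 3.2%–4.0% (half view) are conditional on an assumed shift of 0.25 to 0.5 mmHg. They show how sensitive the test would be and do not estimate what will happen. It would be going too far to conclude that allocation is compromised, that the result will be biased, or that block randomisation must be abandoned.

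**What to change.** 1. Delete the block sizes from both sentences of Section 10.1. State only that allocation is 1:1, web-based, restricted and stratified by institution.
2. Keep the block parameters in a restricted file at the randomisation centre. Because 4 and 6 have already been published, load changed, undisclosed parameters for patients not yet randomised.
3. Optionally, make the new blocks larger or more varied. A 6/8/10 mix cuts the certain calls to under 2% even if discovered, but lowers correct guessing only to 66%.

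The cost is a wording amendment and a new list in the existing web system. With blocks of up to 10, the imbalance within a hospital could reach 5 instead of 3. If that happened at both hospitals in the same direction (75 v 65), the standard error would rise by a factor √[(1/75 + 1/65)/(2/70)] = 1.003, about 0.3%.

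A big-stick rule is an alternative on which statisticians would differ. It lowers average guessing to about 56%, but about 11% of allocations are forced, and these stay hidden only while the limit is unknown. It is not a required change.
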